13. PRIOR AND CONCOMITANT MEDICATIONS

Medications will be presented for the SAF Set and coded to preferred names using the WHO Drug Dictionary.

Medications will be classified as prior, prior concomitant, concomitant, or post-treatment based on start and end dates. See APPENDIX 2 for handling of partial dates for medications. In the case where it is not possible to classify a medication due to missing dates the medication will be classified by the worst case, i.e. concomitant.

A medication is considered to have started prior to the first dose of study medication if indicated to have started prior to the first dose of study medication on the eCRF. If the medication started prior to the first dose of study medication, it is considered to have ended prior to the first dose of study medication if indicated to have ended prior to the first dose of study medication on the eCRF.

...\ITI\ITI-007\MYA11638\Biostatistics\Documentation\SAP\ITI-007-404 SAP Final V1.0 12JUN2019.docx Document: Author:

Version Number:1.0

INTRA-CELLULAR THERAPIES INC. (ITCI)

STATISTICAL ANALYSIS PLAN: PROTOCOL ITI-007-404

Page 22 of 53

A medication is considered to have started after the last dose of study medication if indicated as such on the eCRF, assuming it started after completion of all study procedures and assessment related to the last dose of study medication.

- 'Prior' medications are medications which started and stopped prior to date of first dose of study medication.
- 'Prior concomitant' medications are medications which started prior to and stopped after the date of first dose of study medication.
- 'Concomitant' medications are medications which:
 - started after the date of first dose of study medication and started prior to the date of last dose of study medication,
 - AND stopped after the date of first dose of study medication or were ongoing at the completion of Day 43 post-dose assessments on Day 43 (or last treatment day for subjects who discontinue treatment), or were ongoing after the last dose of study medication (if planned assessments are not performed).
- 'Post-treatment' medications are medications which started after completion of Day 43 post-dose assessments (or after last treatment day for subjects who discontinue treatment).

Prior, prior concomitant, concomitant, and post-treatment medication use will be summarized by PT using frequencies and percentages by treatment group. Medications will be sorted alphabetically by PT in summaries. Subjects with multiple occurrences of a medication in the same PT will only be counted once within the PT for each summary.

During the study, a subject may be treated with zolpidem, benzodiazepines, zopiclone, eszopiclone or zalaplon if taken no more than 3 times per week and only during the Screening Period or first 2 weeks of the On-Treatment Period. The number and percent of subjects in the ITT Set receiving zolpidem, benzodiazepines, zopiclone, eszopiclone or zalaplon and the total number of days on zolpidem, benzodiazepines, zopiclone, eszopiclone or zalaplon will be summarized by treatment group for the Screening Period, for each week during the Ontreatment period (Days 1-8, Days 9-15, Days 16-22, Days 23-29, Days 30-36 and Days 37-43), and for post treatment.

Other medications will be summarized by treatment group and study period if deemed necessary.

14. STUDY MEDICATION EXPOSURE AND TREATMENT COMPLIANCE

Exposure to study medication and treatment compliance will be presented for the ITT and SAF Sets.

The date of first and last study medication administration will be taken from the eCRF's 'Dosing' and 'End of Treatment' forms, respectively. If a discontinued subject is missing the end of treatment date from the 'End of Treatment' form, the last known dispense date will be used as the date of last study medication administration.

Document: ...\ITI\ITI-007\MYA11638\Biostatistics\Documentation\SAP\ITI-007-404 SAP Final V1.0 12JUN2019.docx Author: Version Number:1.0

INTRA-CELLULAR THERAPIES INC. (ITCI)

STATISTICAL ANALYSIS PLAN: PROTOCOL ITI-007-404

Page 23 of 53

Duration of exposure will be summarized by treatment group as a continuous variable, using mean, SD, median, minimum and maximum. In addition, the number and percentage of subjects within each planned Study Week (1-8 days, 9-15 days, 16-22 days, 23-29 days, 30-36 days, 37-43 days, and > 43 days) will be presented.

Compliance with study medication will be derived from the drug return CRF page. For each subject, overall compliance with study medication (%) will be calculated as 100 × (Number of compliant days) / (Number of days in the On-Treatment Period), where a compliant day is defined as any day during the On-Treatment Period on which the subject took 1 capsule, and 'Number of days in the On-Treatment Period' is equivalent to 'Duration of Exposure' as defined above. The number and percentage of compliant and non compliant subjects will be presented. Non-compliant subjects are defined as those subjects with a compliance less than 80% or greater than 120%.

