4 STUDY DESIGN

This is a Phase 3, randomized, double-blind, placebo-controlled, multi-center study to evaluate the efficacy and safety of lumateperone monotherapy in the treatment of patients with major depressive episodes associated with Bipolar I or Bipolar II Disorder (Bipolar Depression). The study consists of the following periods: Screening Period, double-blind On-treatment Period, and Safety Follow-up Period.

Screening Period (2 Weeks)

Potential patients will be evaluated during a Screening Period lasting up to 2 weeks, to ensure sufficient washout of restricted medications. Extension to the screening period may be approved by the Sponsor or representative in extenuating circumstances related to the patient or caregiver.

After obtaining written informed consent, diagnostic interviews and physical examinations will be conducted, vital signs and ECGs will be assessed, and blood samples for laboratory assessments will be collected. Patients considered potentially eligible for participation will be required to discontinue their current antidepressant treatment and/or other psychotropic drugs.

At baseline (Visit 2), patients who continue to meet all eligibility criteria will be randomly assigned to 1 of the 2 treatment arms for a 6-week, double-blind treatment period. Patients will be randomly assigned to 1 of the following groups: 60 mg ITI-007 or matching placebo.

Double-Blind On-Treatment Period (6 Weeks)

Patients will take their first dose of study medication the evening of their baseline visit. A single dose will be taken each day in the evening, with or without food, for the duration of the 6-week On-treatment Period.

Following randomization, patients will attend the clinic on Days 8, 15, 22, 29, 36 and 43.

Safety Follow-up Period (2 Weeks)

A return to the clinic for a safety follow-up visit will occur at Week 8, approximately 2 weeks following the last dose of study medication. If possible, patients who withdraw prematurely will be seen for an early termination visit (within 1 week of early termination) and will be asked to return to the clinic for a safety follow-up visit 2 weeks following withdrawal.

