5.5.2 Handling of Patient Withdrawals or Patient Discontinuation of Study Intervention

Patients are free to withdraw from the study or study treatment at any time. Patient participation in the study may be stopped at any time at the discretion of the investigator or at the request of the sponsor.

Patients who discontinue study treatment or active participation in the study will no longer receive study treatment. When a patient withdraws from the study, the reason(s) for withdrawal shall be recorded by the investigator on the relevant screen of the electronic case report form (eCRF). Whenever possible, all patients who discontinue study treatment or withdraw from the study prematurely will undergo all end-of-study assessments. Patients who fail to return for final assessments will be contacted by the study site (2 documented telephone calls followed by 1 registered letter or similar procedures depending on regional differences) in an attempt to have them comply with the protocol.

It is vital to obtain follow-up data on any patient withdrawn as a result of an AE or serious AE (SAE). In every case, efforts must be made to undertake protocol-specified, safety, follow-up procedures. All data collected from all patients, including early withdrawals, will be used in the reporting and analysis of the study.

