6.1.2 Formulation, Packaging, and Labeling

ITI-007 and matching placebo will be prepared according to current Good Manufacturing Practice standards in carded blister strips and shipped under ambient conditions. Each treatment card will contain a sufficient quantity of capsules for 1 patient for two weeks (14 doses, plus 2 extras), to be dispensed every other visit of the 6-week treatment period. Each ITI-007 dosing container will be labeled according to local laws and regulations.

The dose card for each study treatment will contain two 1×8 strips of over-encapsulated tablets (final product in capsule form) as described in Table 6-.

Treatment	Card Contents
Placebo	Two 1×8 strips of placebo over- encapsulated tablets (8 over- encapsulated tablets/strip)
60-mg ITI-007	Two 1×8 strips of 60-mg ITI-007 over- encapsulated tablets (8 over- encapsulated tablets/strip)

 Table 6-3
 Bi-Weekly Treatment Cards

Note: Each card will hold 16 over-encapsulated tablets in 2 strips of 8.

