6.2 Dosage, Preparation and Administration of Study Product

Patients will be assigned to receive either ITI-007 (60-mg dose) or placebo. Study site personnel will receive a treatment card number from the IVRS/IWRS for each patient at every second clinic visit (e.g. at baseline and Study Days 15 and 29), to ensure that the correct investigational product is dispensed. Patients will self-administer all doses orally, once daily, at home, in the evening for the duration of the on-treatment period. Treatment will be administered with or without food, between approximately 8:00 PM and 10:30 PM, and at approximately the same time each day whenever possible. Treatments will be provided in dose cards containing 2 strips of over-encapsulated tablets. Patients will be instructed to take 1 capsule per dose. Patients will be instructed to bring the bi-weekly treatment card to the study site at the next visit to assess compliance.

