6.5 Assessment of Patient Compliance with Study Product Administration

Patient compliance will be assessed by capsule counts of unused study medication at each visit during the double-blind treatment phase. Any irregularities in medication adherence should be discussed with the patient. Any patient who misses 2 doses of study medication per week in any 2 weeks of the study treatment period or who misses 3 or more doses of study medication in any single week should be considered for early discontinuation. Any exceptions due to unusual circumstances should be discussed on a case-by-case basis with the Medical Monitor to determine whether a patient may continue despite apparent treatment compliance issues.

Dispensing study treatment to be taken by patients in an outpatient study increases risk for medication errors. All errors in medication dispensing or administration must be carefully documented. These errors may include but are not limited to providing the wrong dose (not taking 1 capsule per dose or taking too many capsules per dose), losing medication, or administration at the wrong time of day. Medication adherence will be emphasized at every visit. Written instructions will be provided to the patients with the weekly medication card in order to minimize medication error. Additional adherence procedures may be implemented.

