16. SAFETY OUTCOMES

All outputs for safety outcomes will be based on the SAF Set.

16.1. FOR BY VISIT SUMMARIES OF CHANGE FROM BASELINE SUMMARIES, THE LAST VALUE ON TREATMENT (LAST ASSESSMENT ON OR BEFORE THE LAST DOSE OF STUDY MEDICATION PLUS ONE DAY) WILL BE PRESENTED. ADVERSE EVENTS

Adverse Events (AEs) will be coded using the Medical Dictionary for Regulatory Activities

Document: ...\ITI\ITI-007\MYA11638\Biostatistics\Documentation\SAP\ITI-007-404 SAP Final V1.0 12JUN2019.docx
Author: Version Number:1.0

Version Number:1.0
Version Date: 12JUN2019

Page 31 of 53

(MedDRA) central coding dictionary currently in effect at the time of analysis or database lock.

Treatment emergent adverse events (TEAEs) are defined as AEs that started or worsened in severity on or after the first dose of study medication and on or before the date last dose of study medication plus one day.

All AEs with an onset date after the last dose of study medication plus one day will be listed in the AE data listing and labelled as 'Follow-up Adverse Event'.

See APPENDIX 2 for handling of partial or completely missing dates for AEs. In the case where it is not possible to define an AE as treatment emergent or not due to missing dates, the AE will be classified as the worst case, i.e. treatment emergent.

An overall summary of number of subjects within each of the categories described in the subsections 16.1.1 and 16.1.2 below will be provided as specified in the TLF shells.

Listings will include all AEs, TEAEs and Non-TEAEs. A seperate listing for TEAEs leading to study discontinuation will be presented.

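### For a discontinued subject with no end-of-treatment date, SAP 14 puts the last dose on the last dispensing day, even where a later capsule count shows about six more days of dosing

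*SAP*

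**What the plan says.** SAP 14 takes the last-dose date from the End of Treatment form. If a discontinued subject has no date there, "the last known dispense date will be used as the date of last study medication administration".

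The supply schedule is in the protocol. Each card holds "a sufficient quantity of capsules for 1 patient for two weeks (14 doses, plus 2 extras), to be dispensed every other visit" (Protocol 6.1.2), and Protocol 6.2 places dispensing at baseline, Day 15 and Day 29. Dosing is in the evening: "Patients will take their first dose of study medication the evening of their baseline visit" (Protocol 4).

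Evidence of dosing between dispensing visits is also planned. Protocol 6.5: "Patient compliance will be assessed by capsule counts of unused study medication at each visit during the double-blind treatment phase". SAP 14: "Compliance with study medication will be derived from the drug return CRF page".

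SAP 16.1 ends the treatment-emergent (TEAE) window one day after the last dose and labels later events as follow-up events. Its heading defines the last value on treatment as the "LAST ASSESSMENT ON OR BEFORE THE LAST DOSE OF STUDY MEDICATION PLUS ONE DAY". It also says that an event that cannot be classified because of missing dates is counted as treatment emergent, as the worst case.

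**The concern.** A dispensing date shows that a card was handed over. It does not show when dosing stopped. With evening dosing it normally marks the first dose of that card, so the rule assumes that one dose was taken from a card of 14, even where the subject attended a later visit and the count showed capsules gone. The date is too late only if nothing from the last card was taken.

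Within SAP 14 this shortens exposure. If SAP 16.1 takes the same date, a dated adverse event that began on drug can leave the TEAE incidence tables, and the latest value measured on drug can leave the last-on-treatment summary. That would run against the SAP's own worst-case convention: because a last-dose date has been filled in, the event looks classifiable and, on a plain reading, the convention is not triggered.

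**Working it through.** **Inputs**
- Dispensing days d = 1, 15, 29 (Protocol 6.2), with 14 planned doses per card (Protocol 6.1.2).
- Evening dosing from Day 1 (Protocol 4 and 6.2).
- Mid-card visits v = 8, 22, 36, each ±1 day (protocol contents list, Section 7).
- Window end = last dose + 1 day (SAP 16.1).
- On-treatment laboratory days 8, 22, 43 (SAP 16.2); vital-sign days 8, 15, 22, 29, 36, 43 (SAP 16.4).

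**Schedule check.** 3 cards × 14 doses = 42, which agrees with the 42 on-treatment days in SAP Table A. The gaps 15 − 1, 29 − 15 and 43 − 29 are 14 days each. Each dispensing day is therefore the first dosing day of its card.

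**Subject last seen at a mid-card visit, no missed doses.** The count at visit v supports dosing through the evening of day v − 1.

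| | Last seen Day 8 | Last seen Day 22 | Last seen Day 36 |
|---|---|---|---|
| Last dose under SAP 14 (d) | 1 | 15 | 29 |
| Last evidenced dose (v − 1) | 7 | 21 | 35 |
| Dosing days dropped, (v − 1) − d | 6 | 6 | 6 |
| Window end under SAP 14 (d + 1) | Day 2 | Day 16 | Day 30 |
| Window end on evidence, (v − 1) + 1 | Day 8 | Day 22 | Day 36 |
| Onsets moved to follow-up | Days 3-8 | Days 17-22 | Days 31-36 |
| Last on-treatment lab, SAP 14 / evidence | none / Day 8 | Day 8 / Day 22 | Day 22 / Day 22 |
| Last on-treatment vital signs, SAP 14 / evidence | none / Day 8 | Day 15 / Day 22 | Day 29 / Day 36 |

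**Visit tolerance.** On the first card d is fixed at Day 1, so the days dropped run from (7 − 1) − 1 = 5 to (9 − 1) − 1 = 7. On the second card they run from (21 − 1) − 16 = 4 to (23 − 1) − 14 = 8, and the third card gives the same 4 to 8. The mid-card visit stays outside the window in every combination. The closest cases are Day 7 against Day 2, Day 21 against Day 17, and Day 35 against Day 31.

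**Exposure.** The public text does not show the definition of duration. Assuming last dose − first dose + 1, the rule gives 1 instead of 7 days, 15 instead of 21, and 29 instead of 35. In the SAP 14 bands the first case does not move (both 1-8 days). The second falls from 16-22 to 9-15 days, and the third from 30-36 to 23-29 days.

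**Upper bound.** If the whole card was taken, (d + 13) − d = 13 planned dosing days are dropped, or 15 if both spare capsules were used. A mid-card count alone does not evidence these later doses.

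**The case against.** The strongest objection is that the safety effect rests on text that is not visible. The rule sits under exposure and compliance, and no sentence carries the imputed date into SAP 16.1. SAP Appendix 2, cited for partial and missing event and medication dates, was not among the supplied text. The definition of duration that SAP 14 refers to is not visible either, so text that qualifies the rule may be missing here. The worst-case sentence in SAP 16.1 speaks of missing dates in general and could be read to cover a missing last-dose date. This stands: the TEAE and last-value effects are conditional, and precedence between the two rules is unstated. The wrong date within SAP 14 does not depend on it.

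The trigger is also narrow. It needs an end-of-treatment date still blank at lock and a later attended visit. Protocol 16.2 requires all eCRF fields to be filled in, Protocol 5.4.3 has queries resolved before the code is broken, Protocol 12 plans a blinded review of completeness, and Protocol 5.5.2 requires "2 documented telephone calls followed by 1 registered letter or similar procedures depending on regional differences" for patients who do not return. This stands too, and it keeps the issue small.

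A reader might infer more than the documents support:
- **That a subject last seen at Day 8 has no on-treatment laboratory or vital-sign data at all.** Table A assigns relative Days 2-11 to Day 8 and Days 19-25 to Day 22 with no last-dose condition, so these values stay in the by-visit tables. Only the last-on-treatment summary could lose them.
- **That the comparison between arms is biased.** The rule is the same in both arms, and the documents give no counts by arm.
- **That the worst-case convention should also stretch the window for laboratory and vital-sign values.** SAP 16.1 states it for adverse events only, and stretching it could label an off-drug measurement as on-treatment.

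**Conclusion.** The rule gives a wrong last-dose date whenever a later attended visit and capsule count show dosing past the dispensing day. On the nominal schedule the error is 6 evidenced dosing days; with ±1-day visits it is 5-7 on the first card and 4-8 on the second and third. Understated exposure follows from SAP 14 alone, given the assumed definition of duration.

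The reclassified event onsets and the lost last-on-treatment value hold if SAP 16.1 uses this date. That is the natural reading, because no other last-dose definition is visible, but it is not confirmed. Tables of SAEs and of events leading to discontinuation, by-visit tables and the adverse-event listing are largely unaffected. No visible efficacy analysis uses the date. The number of affected subjects is not given and is probably small. This is a minor issue, worth correcting because the evidence needed is already planned to be collected.

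**What to change.** First check whether SAP Appendix 2 already covers a missing last-dose date. If it does not:

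1. In SAP 14, when the end-of-treatment date is missing, set the last dose to the latest date supported by dosing evidence: the evening before the last attended on-treatment visit at which the capsule count or drug-return record shows continued dosing. Use the dispense date only when no later evidence exists.
2. Use this single date for exposure and for the last-on-treatment value.
3. For TEAE flagging only, state that the worst-case rule in SAP 16.1 takes precedence when the last-dose date is imputed. An event with onset after the evidence-based window, but within the planned supply of the last card, then counts as treatment emergent. The limit is dispense date + 13 days + 1 day, i.e. Day 15, 29 or 43 on the nominal schedule, or an earlier documented stop. This is a classification rule for events and does not create a second last-dose date.

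The cost is a few sentences in the SAP and one derivation; capsule counts and drug-return data are already planned. A few events that began after drug was stopped may be counted as treatment emergent. Counts give numbers of capsules rather than dates, so where doses were missed the evidence date is approximate.

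### The SAP's compliance percentage cannot exceed 100%, so its greater-than-120% limit never applies and it cannot identify over-use as such

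*SAP*

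**What the plan says.** SAP section 14 gives the formula: "overall compliance with study medication (%) will be calculated as 100 × (Number of compliant days) / (Number of days in the On-Treatment Period"). The numerator counts days: "a compliant day is defined as any day during the On-Treatment Period on which the subject took 1 capsule". For the denominator it says "Number of days in the On-Treatment Period' is equivalent to 'Duration of Exposure' as defined above". The stated source is one form: "Compliance with study medication will be derived from the drug return CRF page". The classification rule closes the same paragraph: "Non-compliant subjects are defined as those subjects with a compliance less than 80% or greater than 120" per cent. If a discontinued subject has no end-of-treatment date, "the last known dispense date will be used as the date of last study medication administration". Exposure and compliance are presented for the ITT and Safety sets.

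Protocol 12.4.3 asks for a compliance percentage by treatment group without giving a formula. Protocol 6.5 assesses compliance by counting leftover capsules at visits. Protocol 6.1.2 supplies cards for two weeks ("14 doses, plus 2 extras"), and protocol 6.2 has them dispensed at baseline, Day 15 and Day 29.

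**The concern.** A limit above 100% suits a ratio of capsules taken to capsules due. It does not suit a share of days, which stops at 100%. The paragraph appears to combine a day-based formula with a capsule-based threshold, so half of the non-compliance definition does nothing.

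The formula also leaves open whether a compliant day needs exactly one capsule or at least one. The choice decides how a subject who doubles doses is classified. At stake is whether the compliance table can show over-use, and whether two programmers would produce the same table.

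**Working it through.** The 120% limit is a rule, not a computed result, so the check is whether any dosing pattern can reach it.

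**Inputs**
- Formula, day definition and limits: SAP section 14.
- Capsules per card: 16 (protocol 6.1.2: "Each card will hold 16 over-encapsulated tablets in 2 strips of 8").
- Cards: 3 (protocol 6.2), so 3 × 16 = 48 capsules.
- Treatment period: 6 weeks = 42 days.

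**Step 1: upper bound of the SAP formula.** Let D be days of exposure, s days with one capsule, d days with two and m days with none, so s + d + m = D.
- Exactly one: 100 × s/D ≤ 100%.
- At least one: 100 × (s + d)/D ≤ 100%.

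The bound holds for every D, and days with three or more capsules do not change it. A value above 120% is unreachable on either reading.

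**Step 2: classification of over-use.** The capsule ratio is 100 × (s + 2d)/D.

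| Pattern | D | Capsules | Exactly one | At least one | Capsule ratio |
|---|---|---|---|---|---|
| 5 doubled, 37 single | 42 | 47 | 37/42 = 88.1% | 100% | 47/42 = 111.9% |
| 6 doubled, 36 single | 42 | 48 | 36/42 = 85.7% | 100% | 48/42 = 114.3% |
| 5 doubled, 2 single | 7 | 12 | 2/7 = 28.6% | 100% | 12/7 = 171.4% |
| 6 doubled, 4 single | 10 | 16 | 4/10 = 40.0% | 100% | 16/10 = 160.0% |
| 10 doubled, 22 single, 10 missed | 42 | 42 | 22/42 = 52.4% | 32/42 = 76.2% | 42/42 = 100% |

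The third and fourth rows are over-users. They are flagged as low on one reading, called compliant on the other, and flagged as high by a capsule ratio.

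**Step 3: when the lower limit catches over-use (exactly one).** Over 42 days, 8 deviating days give 34/42 = 81.0%, which is compliant; 9 give 33/42 = 78.6%, which is flagged. Doubling on 9 days without a miss needs 42 + 9 = 51 capsules, more than the 48 supplied. A completer who misses no day can double on at most 48 − 42 = 6 days and is called compliant on both readings.

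**Step 4: whether a capsule ratio would revive the 120% limit.** Exceeding it over 42 days needs more than 1.2 × 42 = 50.4 capsules, so at least 51. With 48 capsules the maximum is 48/42 = 114.3%, 48/41 = 117.1%, 48/40 = 120.0% (not above the limit) and 48/39 = 123.1%. With one card it is 16/14 = 114.3% and 16/13 = 123.1%. The limit would act only on shorter exposures.

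**Step 5: the fallback date.** On the literal text a compliant day must lie within the On-Treatment Period, so the 100% bound survives. If a program shortened only the denominator, last dispensing on Day 15 with 22 dosed days would give 22/15 = 147%. That would be an artefact, not a measure of over-use.

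**The case against.** Three stronger conclusions are tempting, and the documents support none of them.

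- *A reader might infer that over-use goes undetected in the trial.* It does not. Protocol 6.3 sends every overdose to the Medical Monitor, whether or not an adverse event accompanies it, and protocol 6.5 has dosing errors, including excess capsules, documented. On the exactly-one reading, heavy over-use can also fall below 80% and be flagged, though under the wrong label.
- *A reader might infer that the formula cannot be computed from the drug return page.* That page is not in the documents. The capsule counting in protocol 6.5 makes a bare count likely, and a bare count would not show what was taken on each day. Whether the page also records missed or multiple-dose days is unknown.
- *A reader might infer that an analysis set inherits the problem.* The ITT and Safety definitions do not use the flag. The per-protocol deviation criteria are deferred to the SAP, and their text there is not visible.

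It can also be objected that a capsule ratio has faults of its own. This stands. Five doubled days in 42 still scores 112% and counts as compliant. Missed and doubled days cancel, as the last table row shows. A subject who stops on Day 5 and keeps the card scores 16/5 = 320%. The fallback date can shrink the denominator further. These points limit the repair; they do not rescue the present wording.

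**Conclusion.** The inconsistency is real and minor. As written, the compliance percentage is capped at 100%, the greater-than-120% limit has no effect, and the percentage cannot identify over-use as such.

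The visible consequence is confined to the descriptive compliance table for the ITT and Safety sets. No visible text links it to the primary or key secondary analysis.

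The 100% cap rests only on the SAP's wording and holds on both readings of one capsule. The supply figures assume the three standard cards with no replacements. The SAP refers to a definition of duration of exposure that does not appear in the text available; it may have been removed, so no finding is made on it.

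**What to change.** Reconcile formula and threshold in SAP section 14 in one of two ways.

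1. **Capsule ratio.** Define compliance as 100 × (capsules dispensed − capsules returned) / days of exposure, which matches the counting in protocol 6.5. Set to missing, or report separately, subjects with unreturned cards and subjects whose last-dose date is the fallback dispense date. Review the 120% limit at the same time, since the standard supply keeps a 42-day completer at or below 114%.
2. **Day count.** Keep the present formula, state that one capsule means exactly one, confirm that the drug return page holds day-level data, drop the 120% limit and tabulate over-use separately.

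The cost is a few sentences in the SAP and one derivation. Protocol section 12 allows changes of analysis method to be documented in the SAP without a protocol amendment. The price of option 1 is that lost capsules count as taken and that missed and doubled days offset each other. Option 2 avoids the offsetting but depends on data that a capsule count alone would not supply.
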